**Table 3. Protocol-Required Laboratory Assessments**

Assessment	Description
	
 
• Urine
 
• Semen
 

Hepatitis B and Hepatitis C (CL)	
 
• Hepatitis B Surface Antigen
 
• Total Hepatitis B Core Antibodies
 
• HBV DNA
 
• Hepatitis C Virus Antibodies
 
• HCV RNA
 

α-Fetoprotein (CL)	
 
• Pre-existing liver disease
 

HIV Serology (CL)	
 
• HIV-1/HIV-2 Antibody Screen
 

HIV Viral load and CD4 (CL)	
 
• HIV-1 Qualitative, RNA
 

Spare Plasma (CL)	
 
• Aliquoted from already collected blood samples
 

PAXgene (CL)	
 
• RNA extraction and transcriptomic assays
 

Day 1 Banked Biospecimen (CL)	
 
• Pharmacogenomics
 

AAV = adeno-associated virus vector; ALP = alkaline phosphatase; ALT = alanine aminotransferase; aPTT = ; AST = aspartate transaminase; BUN = blood urea nitrogen; CL = Central laboratory; ELISPOT = enzyme-linked immunospot assay; FIX = coagulation factor IX; GGT = gamma-glutamyl transferase; HBV DNA = hepatitis B deoxyribonucleic acid; HCV RNA = hepatitis C virus ribonucleic acid; HDL = high density lipoprotein; HIV = human immunodeficiency virus; IFN-γ = interferon gamma; INR = international normalized ratio; LDH = lactate dehydrogenase; LDL = Low-density lipoprotein; LL = Local laboratory; PBMC = peripheral blood mononuclear cells; RBC = red blood cells; ROTEM = rotational thromboelastogram; TAT = thrombin-antithrombin; TEG = thromboelastography; TGA = thrombin generation assay; VLDL = very-low-density lipoprotein; WBC = white blood cells

Investigators must document their review of each laboratory safety report.

### 10.3. Appendix 3: Adverse Events: Definitions and Procedures for Recording, Evaluating, Follow-up, and Reporting

#### 10.3.1. Definition of AE

AE Definition

 
• An AE is any untoward medical occurrence in a patient or clinical study participant, temporally associated with the use of study intervention, whether or not considered related to the study intervention.
 
• NOTE: An AE can therefore be any unfavorable and unintended sign (including an abnormal laboratory finding), symptom, or disease (new or exacerbated) temporally associated with the use of study intervention.
 

Events Meeting the AE Definition

 
• Any abnormal laboratory test results (hematology, clinical chemistry, or urinalysis) or other safety assessments (eg, ECG, radiological scans, vital signs measurements),
 

including those that worsen from baseline, considered clinically significant in the medical and scientific judgment of the investigator (ie, not related to progression of underlying disease).

- Exacerbation of a chronic or intermittent pre-existing condition including either an increase in frequency and/or intensity of the condition.
- New conditions detected or diagnosed after study intervention administration even though it may have been present before the start of the study.
- Signs, symptoms, or the clinical sequelae of a suspected drug-drug interaction.
- Signs, symptoms, or the clinical sequelae of a suspected overdose of either study intervention or a concomitant medication. Overdose per se will not be reported as an AE/SAE unless it is an intentional overdose taken with possible suicidal/self-harming intent. Such overdoses should be reported regardless of sequelae.
- “Lack of efficacy” or “failure of expected pharmacological action” per se will not be reported as an AE or SAE. Such instances will be captured in the efficacy assessments. However, the signs, symptoms, and/or clinical sequelae resulting from lack of efficacy will be reported as AE or SAE if they fulfil the definition of an AE or SAE.
- The signs, symptoms, and/or clinical sequelae resulting from lack of efficacy will be reported as AE or SAE if they fulfil the definition of an AE or SAE. Also, “lack of efficacy” or “failure of expected pharmacological action” also constitutes an AE or SAE.
- “Lack of efficacy” or “failure of expected pharmacological action” per se will not be reported as an AE or SAE. Such instances will be captured in the efficacy assessments. However, the signs, symptoms, and/or clinical sequelae resulting from lack of efficacy will be reported as AE or SAE if they fulfil the definition of an AE or SAE.

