**3. OBJECTIVES, ESTIMANDS AND ENDPOINTS**

Objectives	Endpoints
Primary	

 
The primary objective is to evaluate the safety and tolerability of a single IV infusion of PF-06838435 in hemophilia B participants ≥18 years of age with ≤2 IU/dL [≤2 %] endogenous factor IX [FIX].
 
	
Clinically significant changes from baseline in the following:
 
 
Physical examination
 
Vital signs
 
Laboratory values
 
Incidence of drug-related adverse events (including inhibitor development)
 
FIX incremental recovery (time at maximum activity [Tmax] and percent recovery for FIX activity)
 
Immune response against AAV capsid protein
 
Immune response against hFIX transgene
 
 
For those individuals who develop hepatic transaminases (ALT and/or AST) elevation of approximately 1.5-fold or successively increasing during follow-up above baseline (or vector-derived FIX:C activity levels decline without evidence of FIX inhibitor, accompanied by rising IFN ELISPOTs on PBMCs) after PF-06838435 infusion, treatment with corticosteroids will be instituted. Alternative immunosuppressive

	
therapies will be considered if the initial corticosteroid treatments are not successful.
 
For any individual who reaches >150% vector-derived FIX:C activity levels after the infusion of PF-06838435, laboratory parameters of thrombotic potential will be assessed.

Secondary	

• The secondary objective is to characterize the kinetics of PF-06838435.

	

• Vector-derived FIX:C activity levels:

• Peak

• Steady-state

• FIX antigen levels

CCI
 	

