### 10.3.2. Definition of SAE

If an event is not an AE per definition above, then it cannot be an SAE even if serious conditions are met (eg, hospitalization for signs/symptoms of the disease under study, death due to progression of disease).

A SAE is defined as any untoward medical occurrence that, at any dose:
a. Results in death
b. Is life-threatening The term 'life-threatening' in the definition of 'serious' refers to an event in which the participant was at risk of death at the time of the event. It does not refer to an event, which hypothetically might have caused death, if it were more severe.
c. Requires inpatient hospitalization or prolongation of existing hospitalization In general, hospitalization signifies that the participant has been detained (usually involving at least an overnight stay) at the hospital or emergency ward for observation and/or treatment that would not have been appropriate in the physician's office or outpatient setting. Complications that occur during hospitalization are AEs. If a complication prolongs hospitalization or fulfills any other serious criteria, the event is serious. When in doubt as to whether "hospitalization" occurred or was necessary, the AE should be considered serious. Hospitalization for elective treatment of a pre-existing condition that did not worsen from baseline is not considered an AE.
d. Results in persistent disability/incapacity 

• The term disability means a substantial disruption of a person's ability to conduct normal life functions.

• This definition is not intended to include experiences of relatively minor medical significance such as uncomplicated headache, nausea, vomiting, diarrhea, influenza, and accidental trauma (eg, sprained ankle) which may interfere with or prevent everyday life functions but do not constitute a substantial disruption.

e. Is a congenital anomaly/birth defect

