9.1. Adverse Events

An adverse event (AE) is any untoward, undesired, or unplanned medical occurrence in the form of any unfavorable and unintended sign (including clinically significant abnormal laboratory finding), symptom, or disease temporally associated with the use of the study drug, regardless of causal relationship, occurring in a subject participating in a clinical study. In this study, bleeding episodes are not considered AEs, but bleeding episodes that meet the criteria of serious are to be reported as serious adverse events (SAEs). Adverse events will be classified using the Medical Dictionary for Regulatory Activities (MedDRA) System Organ Classes and Preferred Terms. MedDRA version 18.0 will be used through-out the study.

An adverse event will be regarded as treatment emergent AE (TEAE) if the start date is on or after the infusion of PF-06838435 but before subject's last visit on study (or the date of withdrawal/the date of being lost to follow-up). We will use the below algorithm to derive the start date for the determination of treatment emergence when start date is partially/completely missing and the original dates will be displayed in the listings:

- If year is missing (or completely missing) then set to the PF-06838435 infusion date
- If (year is present, and month and day are missing)
 - If year = year of PF-06838435 infusion date: then set to the PF-06838435 infusion date
 - If year < year of PF-06838435 infusion date: set month and day to December 31st
 - If year > year of PF-06838435 infusion date: set month and day to January 1st
- If month and year are present and day is missing:
 - If year = year of PF-06838435 infusion date, and:
 - month = month of PF-06838435 infusion date: set day to day of SPK-9001 infusion date
 - If month < month of PF-06838435 infusion date: set day to last day of month.
 - If month > month of PF-06838435 infusion date: set day to 1st day of month
 - If year < year of PF-06838435 infusion date: set day to last day of month.

- If year > year of PF-06838435 infusion date: set day to 1st day of month.

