9.1.2. Relationship of Adverse Events to Study Drug

A summary of TEAEs by relationship to study drug will be presented by dose group in a table. The investigator will provide an assessment of the relationship of the event to the study drug. The possible relationships are “Not Related”, “Unlikely”, “Possible”, and “Related”. In the TEAE relationship table, if a subject reported multiple occurrences of the same TEAE, only the most closely related occurrence will be presented. TEAEs that are missing a relationship or with a relationship other than “Not Related” or “Unlikely” will be presented in the summary table as “Related” but will be presented in the data listing with a missing relationship or the actual relationship respectively. Percentages will be based on the number of subjects within each dose group in the safety analysis set.

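### Protocol 10.3.1 says both that lack of efficacy is not an AE/SAE and that it is, and SAP 9.1 has no rule that settles it

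*Protocol*

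**What the plan says.** Protocol 10.3.1 (Appendix 3) lists the events that meet the AE definition. Three consecutive bullets in that list deal with lack of efficacy, or a drug that does not act as expected:

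- First bullet: it "per se will not be reported as an AE or SAE. Such instances will be captured in the efficacy assessments". Sequelae are reported if they meet the AE or SAE definition in their own right.
- Second bullet: sequelae are reported on the same terms, but lack of efficacy itself "also constitutes an AE or SAE".
- Third bullet: repeats the first.

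Protocol 10.3.2 then makes SAE status depend on AE status: "If an event is not an AE per definition above, then it cannot be an SAE even if serious conditions are met".

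Protocol 3 and SAP 3.2.1 both list the incidence of drug-related AEs among the primary endpoints.

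SAP 9.1 gives a general definition, beginning "An adverse event (AE) is any untoward, undesired, or unplanned medical occurrence in the form of any unfavorable and unintended sign". It adds a specific rule for bleeds, "In this study, bleeding episodes are not considered AEs", with serious bleeds reported as SAEs. It has no corresponding rule for lack of efficacy.

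**The concern.** The two rules cannot both be followed. A site that reads the first bullet leaves a participant with low or vanishing FIX activity out of the AE record. A site that reads the second enters the same participant as an AE, and as an SAE if a seriousness criterion is thought to be met. Both sites comply with the protocol.

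The situation is foreseeable. The Synopsis rationale describes an earlier AAV8 study in which two of three participants kept expression for only about 2 to 4 months and the third declined over about 18 months. Protocol 4.3 reports no detectable FIX in several low-dose participants of two other vector trials. Under Protocol 4.1.3.1 a dose level may still expand when up to 2 of 5 participants, and later up to 4 of 10, are not above 5% activity.

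At stake is whether the safety tables of a first-in-human gene therapy count the same thing at every site.

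**Working it through.** The documents give no figure to reproduce: the study is descriptive, with no hypothesis test. The check has three parts.

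**1. Does anything in the documents resolve the conflict?**

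- The three bullets carry no qualifier by seriousness, timing or product.
- The list in Protocol 10.3.1 of events that do not meet the AE definition does not mention lack of efficacy.
- Protocol 8.3.6 covers bleeding only.
- SAP 9.1 covers bleeding only, beyond its general definition.

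Nothing resolves it. Bleeds have their own rules, and sequelae that meet the AE definition are reportable under all three bullets. The ambiguity is therefore confined to poor or lost FIX expression by itself.

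**2. Which outputs would such a report reach?**

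- *All-TEAE tables (SAP 9.1.1):* reached whatever the relatedness.
- *Drug-related tables (SAP 9.1.2):* "TEAEs that are missing a relationship or with a relationship other than" Not Related or Unlikely are tabulated as Related. The report enters if it is rated Possible or Related, or if the rating is missing.
- *Toxicity-grade table (SAP 9.1.4):* a TEAE without a grade is shown as Grade 4. In the Protocol 10.8 scale the only coagulation row is FIX inhibitor. Low FIX activity without an inhibitor has no row, and Protocol 10.3.3 asks for a grade only where one applies. An ungraded report would therefore appear as Grade 4.
- *SAE reporting (Protocol 8.3.1.1 and 10.3.2):* AE status is the gateway to SAE status and to the 24-hour reporting duty.

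**3. How far could subject-level drug-related incidence move?**

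Two conditions must both hold: the report counts as related (including a missing rating), and the participant has no other drug-related AE. Each such participant then moves incidence by 1/n.

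| n | Source | 1/n |
|---|---|---|
| 5 | initial dose group, Protocol 4.1.3.1 | 1/5 = 20.0 points |
| 15 | SAP 3.1 | 1/15 = 6.7 points |
| 20 | Protocol 9.2 | 1/20 = 5.0 points |
| 30 | SAP 4.1 | 1/30 = 3.3 points |

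The planned totals differ between sections, so a range is shown. SAP 9.1.2 takes percentages within dose group, so the dose-group size is the operative denominator.

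Illustration, **assuming** two such participants and no other related AE, with exact (Clopper-Pearson) 95% intervals:

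- n=5: 0/5 = 0% (0 to 52.2) if excluded; 2/5 = 40% (5.3 to 85.3) if included.
- n=20: 0/20 = 0% (0 to 16.8) if excluded; 2/20 = 10% (1.2 to 31.7) if included.

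**The case against.** The strongest reply is that the conflict is real but its effect is small and visible.

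- There is no hypothesis test, and the safety analysis is descriptive. Escalation and expansion in Protocol 4.1.3.1 turn on FIX activity and safety review, not on AE incidence. None of the suspension events in Protocol 4.3.1 names lack of efficacy.
- FIX activity and antigen are secondary endpoints, so low expression is reported under either reading. AEs are listed and tabulated by preferred term, so a lack-of-efficacy term could be picked out.
- The causality categories in Protocol 10.3.3 describe a reaction to the product, which fits the absence of an effect poorly.
- Loss of expression from a capsid immune response may come with raised transaminases (Protocol 10.6). If those are already a related AE, subject-level incidence does not change.
- Protocol 10.3.1 excludes laboratory findings that belong to the underlying disease, which a site might apply to a low FIX value.

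Most of this stands, and it limits the size. It does not remove the conflict. The underlying-disease exclusion does not mention lack of efficacy, whereas the second bullet addresses it directly. Being able to find a term in a listing does not help where another site never recorded the event.

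A reader might infer more: that sites are bound to diverge, that every reclassified participant shifts the primary incidence by 5.0 to 6.7 points, or that two cases among 15 (13.3%) are to be expected. The documents support none of these. Divergence is possible, not certain. The shift depends on the two conditions above. No document predicts a number of cases.

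**Conclusion.** The point holds as an internal inconsistency that should be corrected. The current Protocol 10.3.1 gives two incompatible rules, and neither the rest of the protocol nor SAP 9.1 chooses between them. Exposure is certain for the all-TEAE counts and the toxicity-grade table if any site follows the second bullet. It is possible for SAE reporting and conditional for the primary drug-related incidence.

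Under those conditions the movement per participant runs from 3.3 points (n=30) to 20 points (a dose group of 5). If the participant already has another drug-related AE, only event counts and the system-organ-class and preferred-term rows change. The second bullet looks like a template alternative left in place, but that is inference. The documents do not say which rule was meant.

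**What to change.** Reconcile the three bullets to a single rule. The smallest edit is to delete the sentence saying that lack of efficacy "also constitutes an AE or SAE", together with the duplicate third bullet. Nothing is lost, because FIX activity and antigen are already secondary endpoints and sequelae that meet the AE definition stay reportable. If the sponsor intended the opposite rule, the other two bullets must change instead, and SAP 9.1.4 should say how an event with no row in the toxicity scale is graded.

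In either case, add one line to SAP 9.1 stating the rule and how any lack-of-efficacy events already recorded will be tabulated. The schema note in Protocol 1.2 refers to the study's course before Amendment 7, so existing AE records should be checked.

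The cost is a protocol text change with its usual approval, one SAP line and a review of existing AE records. No new data are needed.

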#### **Events NOT Meeting the AE Definition**

- Any clinically significant abnormal laboratory findings or other abnormal safety assessments which are associated with the underlying disease, unless judged by the investigator to be more severe than expected for the participant’s condition.
- The disease/disorder being studied or expected progression, signs, or symptoms of the disease/disorder being studied, unless more severe than expected for the participant’s condition.
- Medical or surgical procedure (eg, endoscopy, appendectomy): the condition that leads to the procedure is the AE.
- Situations in which an untoward medical occurrence did not occur (social and/or convenience admission to a hospital).
- Anticipated day-to-day fluctuations of pre-existing disease(s) or condition(s) present

or detected at the start of the study that do not worsen.

### 10.3.2. Definition of SAE

If an event is not an AE per definition above, then it cannot be an SAE even if serious conditions are met (eg, hospitalization for signs/symptoms of the disease under study, death due to progression of disease).

A SAE is defined as any untoward medical occurrence that, at any dose:
a. Results in death
b. Is life-threatening The term 'life-threatening' in the definition of 'serious' refers to an event in which the participant was at risk of death at the time of the event. It does not refer to an event, which hypothetically might have caused death, if it were more severe.
c. Requires inpatient hospitalization or prolongation of existing hospitalization In general, hospitalization signifies that the participant has been detained (usually involving at least an overnight stay) at the hospital or emergency ward for observation and/or treatment that would not have been appropriate in the physician's office or outpatient setting. Complications that occur during hospitalization are AEs. If a complication prolongs hospitalization or fulfills any other serious criteria, the event is serious. When in doubt as to whether "hospitalization" occurred or was necessary, the AE should be considered serious. Hospitalization for elective treatment of a pre-existing condition that did not worsen from baseline is not considered an AE.
d. Results in persistent disability/incapacity 

• The term disability means a substantial disruption of a person's ability to conduct normal life functions.

• This definition is not intended to include experiences of relatively minor medical significance such as uncomplicated headache, nausea, vomiting, diarrhea, influenza, and accidental trauma (eg, sprained ankle) which may interfere with or prevent everyday life functions but do not constitute a substantial disruption.

e. Is a congenital anomaly/birth defect
f. Other situations: 

• Medical or scientific judgment should be exercised in deciding whether SAE reporting is appropriate in other situations such as important medical events that may not be immediately life-threatening or result in death or hospitalization but may jeopardize the participant or may require medical or surgical intervention to prevent one of the other outcomes listed in the above definition. These events should usually be considered serious.

 Examples of such events include invasive or malignant cancers, intensive treatment in an emergency room or at home for allergic bronchospasm, blood dyscrasias or convulsions that do not result in hospitalization, or development of drug dependency or drug abuse. In this study, the following events are considered medically important and must be reported as SAEs:

- Any drug-related death during the study;
- Any subject develops drug-related or possibly drug-related Grade III-IV toxicity such as FIX inhibitor, allergic reaction (bronchospasm and anaphylaxis), excluding elevated transaminases ([Section 10.8](#));
- Any subject develops drug-related or possibly drug-related Grade III-IV elevated hepatic transaminases that fails to improve or resolve within four weeks on the immunosuppressive regimens ([Section 10.8](#));
- Any subject develops drug-related or possibly drug-related Grade IV (>10-fold) elevated transaminases ([Section 10.8](#));
- Any subject reaches >150% of normal vector-derived FIX:C activity levels and develops drug-related or possibly drug-related thrombotic event (with the exception of IV infusion-site thrombophlebitis) or if any subject develops a sustained (defined as > 6 weeks) FIX activity levels of > 150%;
- Any occurrence of a malignancy at any point after vector infusion that is possibly, probably, or definitely related to the investigational product.

Participants will be informed of early symptoms and signs of thrombotic phenomena, including pain and/or tenderness along a vein, swelling of an arm or leg without pain or tenderness, redness along a vein, low fever without any known reason (such as a cold or flu), sudden shortness of breath or difficulty breathing or coughing, sudden chest pain, sudden severe headache or changes in vision, and numbness or tingling in arms or legs. If such an event occurs while the subject is at home, the subject will be instructed to seek immediate medical care.

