13. LFTs – albumin, total bilirubin, direct bilirubin, indirect bilirubin, alkaline phosphatase (ALP), aspartate aminotransferase (AST), alanine aminotransferase (ALT), total protein, gamma-glutamyl transferase (GGT), and lactate dehydrogenase (LDH);

Immunology - CPT™ for PBMC by ELISPOT and PAXgene for RNA. PAXgene samples will be stored for analysis at the end of study.

14. Hepatic transaminases and FIX transgene expression will be monitored twice-weekly or thrice-weekly to detect early changes. Between Weeks 1 and 12 post-vector infusion, monitoring will include LFTs, FIX:C, FIX Ag, CPT™ for PBMC by ELISPOT and PAXgene for RNA. Spare plasma, from already collected blood samples will be stored for repeat or additional tests. Some participants may need more frequent monitoring using unscheduled visits.
15. Activated partial thromboplastin time (aPTT) measured in seconds; TAT will be taken just prior to the infusion of FIX product.
16. Participants should be advised to temporarily suspend prophylaxis regimen after vector infusion until being advised by the Investigator to resume.
17. At Day 0, participants should arrive at the clinic with at least 96 hours (4 days) washout of pd-FIX/rFIX or up to 168 hours (7 days) washout of extended half-life FIX product. Participants will receive a single IV infusion of 100 IU/kg of FIX protein product over 10 (±2) minutes.
18. Blood samples will be collected at pre-infusion, 10 (±2) minutes, 1 hour ± 10 minutes, 3 hours ± 10 minutes, 6 hours ± 10 minutes, and 24 (±1) hours from the start-of-infusion of FIX protein product.
19. Thromboelastography (TEG) and/or rotational thromboelastogram (ROTEM) – Only selected participants at selected sites capable of performing these tests locally.  
CCI  
Blood samples will be collected at pre-infusion and 10 (±2) minutes from the start-of-infusion of FIX protein product on Day 0 and End-of-Study Visits.
20. After the completion of FIX protein product infusion, participants will receive PF-06838435 infused via infusion pump over a period of approximately 60 minutes.
21. Haem-A-QoL, EQ-5D-5L, McGill pain questionnaire, and Hemophilia Activities List (including Changes in Level of Activity) questionnaires will be completed by the participants.  
CCI  
[REDACTED]
23. Immunomodulation See [Appendix 2](#): possible tests below:  
LFT – albumin, total bilirubin, direct bilirubin, indirect bilirubin, ALP, AST, ALT, total protein, GGT, and LDH;  
Coagulation –aPTT, FIX:C, FIX Ag  

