### **8.3.6. Disease-Related Events and/or Disease-Related Outcomes Not Qualifying as AEs or SAEs**

The disease related events (DREs) for this study include episodes of bleeding related to hemophilia B. The bleeding episode itself is not reported as an AE, unless the bleeding episode meets the criteria outlined below.

Consideration on whether the bleeding event is a DRE is based on investigator determination and bleeding events recorded by the participant in their electronic diary will be reviewed by the investigator and assessed against reporting obligations for S/AE.

Bleeding, not due to the participant's hemophilia, will be recorded as an AE, and not a DRE.

If any of the following conditions apply, then the event must be recorded and reported as an AE or SAE (instead of a DRE):

- Bleeding events that require hospitalization or meet other SAE criteria ([Section 10.3](#)) should be reported as SAEs. When bleeding episodes that meet the SAE criteria are recorded on the AE CRF, the location (site) of the bleed and the etiologic classification as spontaneous or traumatic should be included.
- The bleeding event is, in the investigator's opinion, of greater intensity, frequency, or duration than expected for the individual participant.

OR

- The investigator considers that there is a reasonable possibility that the bleeding event was related to study intervention.

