9.1.7. Death

All subject deaths during the study will be listed. Deaths will be identified from the AE with “Outcome” recorded as “Fatal” on the AE eCRFs.

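### A serious hemophilia bleed judged unrelated and of expected severity is an SAE under Protocol 8.3.6 and SAP 9.1 but cannot be one under Protocol 10.3.1/10.3.2, and the SAP death listing depends on which rule a site follows

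*Protocol*

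**What the plan says.** **Protocol 8.3.6** treats hemophilia bleeds as disease-related events (DREs) by default: "The bleeding episode itself is not reported as an AE, unless the bleeding episode meets the criteria outlined below". If a listed condition applies, "then the event must be recorded and reported as an AE or SAE (instead of a DRE"). The first condition stands on its own: "Bleeding events that require hospitalization or meet other SAE criteria" are to be reported as SAEs, with a pointer to Section 10.3. Greater than expected intensity, frequency or duration, and a possible relation to study intervention, are separate bullets.

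**Protocol 10.3.1**, in its list of events that are not AEs, includes "The disease/disorder being studied or expected progression, signs, or symptoms of the disease/disorder being studied", with one exemption, for events more severe than expected for that participant.

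**Protocol 10.3.2** opens with a conditional rule. For an event that is not an AE under 10.3.1, "it cannot be an SAE even if serious conditions are met (eg, hospitalization for signs/symptoms of the disease under study". Its second example is death from disease progression.

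**SAP 9.1** agrees with 8.3.6: bleeds are not AEs, but serious bleeds are SAEs. **SAP 9.1.6** builds SAEs from reported AEs. **SAP 9.1.7** promises a listing of every death on study and names one source: "Deaths will be identified from the AE with" a fatal outcome on the AE form.

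**The concern.** Bleeding is the cardinal sign of the disease under study, so the first example in 10.3.2 fits a hospitalised bleed directly. Protocol 8.3 sends sites to Appendix 3 for the AE and SAE definitions, and 8.3.6 itself points to Section 10.3. A site that follows either reference meets a sentence that can cancel what 8.3.6 requires. Appendix 3 does not refer back to 8.3.6.

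Safety is the primary objective, and the period of interest is one in which bleeds can be expected: "Participants should be advised to temporarily suspend prophylaxis regimen after vector infusion" until the investigator advises resuming (Schedule of Activities, note 16). The same event could be reported to the sponsor within 24 hours at one site and not recorded as an AE at another. That would make the SAE tables inconsistent between sites and could change the safety data that reach the DMC.

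**Working it through.** The documents give no figure that depends on these definitions, so the check is to apply each rule to the same event.

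**Step 1. Three types of hospitalised bleed**

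- *More severe than expected.* 8.3.6: SAE. 10.3.1: the exclusion is lifted, since it covers "signs, or symptoms of the disease/disorder being studied, unless more severe than expected" only up to that limit, so 10.3.2 does not apply. No conflict.
- *Possibly related to study intervention.* 8.3.6: reportable under its own bullet as well as under the hospitalisation bullet. If fatal and drug-related, 10.3.2(f) also names it as an SAE that must be reported. The point made here does not rely on this group.
- *Unrelated and of expected severity.* 8.3.6: SAE, because hospitalisation alone is enough. 10.3.1: not an AE. 10.3.2: therefore cannot be an SAE. **Conflict.**

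The third type is the gap. It exists because 8.3.6 makes seriousness sufficient, while 10.3.1 makes unexpected severity necessary.

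**Step 2. Is precedence stated?** No visible text says whether 8.3.6 or Appendix 3 governs. Neither 10.3.1 nor 10.3.2 mentions bleeding events or cites 8.3.6.

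**Step 3. Follow the event into the SAP.** SAP 9.1 states the same rule as 8.3.6, but the SAP can only analyse what sites record. SAP 9.1.6 starts from events reported as AEs, so an event withheld under 10.3.2 does not reach the SAE tables.

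**Step 4. Follow a death.** If a site classes a fatal event as disease progression and of expected severity, 10.3.1/10.3.2 produce no AE record. SAP 9.1.7 then has nothing to select. The death might still appear as a discontinuation reason in the disposition summary (SAP 5.1), but that summary does not feed the death listing.

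**Step 5. Scale.** One participant whose only SAE is omitted changes SAE incidence by 1/n:

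- n = 20 (Protocol 9.2): 1/20 = 5.0 percentage points
- n = 15 (SAP 3.1): 1/15 = 6.7 percentage points
- n = 30 (SAP 4.1, upper limit): 1/30 = 3.3 percentage points

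This is the weight of one participant, not an estimate of how often it would happen. The documents give no rate of hospitalised bleeds.

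**The case against.** The best reply is that the intent is clear. Both texts that deal specifically with bleeds, Protocol 8.3.6 and SAP 9.1, say that serious bleeds are SAEs. Sections 10.3.1 and 10.3.2 are general wording, and the Amendment 7 summary lists them among the sections that took common-template language. Most sites would probably follow 8.3.6. In that case the event goes on the AE form and SAP 9.1.7 finds it. This stands as a statement of likely intent. It does not settle the conflict, because sites are sent to Appendix 3 for the definitions and no rule tells them to set it aside.

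A reader might also infer more than the documents support:

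- *That 10.3.2 bars every hospitalised or fatal bleed from being an SAE.* It does not. The rule applies only to events that are not AEs, and 10.3.1 exempts those more severe than expected.
- *That fatal bleeds will be lost.* Protocol 2.2.2 calls intracranial hemorrhage a leading cause of death, but such an event is the least likely to be judged of expected severity, and an acute fatal hemorrhage is not plainly disease progression. Several judgements must coincide before a death is missed.
- *That the primary endpoint is distorted.* The named endpoint is the incidence of drug-related AEs (Protocol 3, SAP 3.2.1). The bleeds in the gap are those judged unrelated.
- *That the entry criterion for on-demand participants, at least 4 bleeds in 52 weeks or chronic arthropathy, shows the gap will be common.* It concerns bleeds of any kind, not hospitalised ones.

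**Conclusion.** The contradiction is real and narrow. For a serious hemophilia bleed judged unrelated and no more severe than expected, two protocol rules give opposite answers, with no stated precedence. The SAP takes one side but cannot recover events that sites did not record. What is affected is 24-hour SAE reporting, the general SAE tables and, in a rarer case, the death listing. The loss arises only if a site applies Appendix 3 literally. For a death, it also requires that the event be classed as progression.

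SAP 9.1.7 deserves correction in its own right: it promises all deaths but takes them from one type of record. The study is descriptive, so no test or sample size depends on this. It should be corrected because the safety tables of a study of about 20 participants are read case by case.

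**What to change.** 1. In Protocol 10.3.1, add to the disease-symptom bullet: *except bleeding events, which follow Section 8.3.6*.
2. Add the same words to the opening sentence of Protocol 10.3.2. Deleting its two examples would not be enough, because the 10.3.1 exclusion and the conditional rule would remain in force.
3. In SAP 9.1.7, identify deaths from every source that records one (AE page, SAE form, disposition) and reconcile the sources before database lock.

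SAP 9.1 already agrees with 8.3.6 and needs no change. The cost is two short insertions in the protocol appendix, one sentence in the SAP and a simple cross-check of records. Design and treatment are untouched. The reported SAE rate may come out slightly higher.
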